6.2.2 Treatment period

Each subject is expected to participate in 2 treatment periods, i.e. Visit 2 and 3. Subjects that take part in Part 1 cannot take part in Part 2 and vice versa.

Part 1

In the morning of Day 1 of Visit 2 and of Day 22 Visit 3, study participants will be admitted to the trial site and kept under close medical surveillance for at least 38 h following drug administration. In addition subjects will be admitted to the trial site prior to the first dose of donepezil (evening of Day 1 Visit 3) and remain under close medical surveillance until the following morning (Day 2, Visit 3). The subjects will then be allowed to leave the trial site

after formal assessment and confirmation of their fitness. On all other study days, subjects will be treated in an ambulatory fashion.

Part 2

Study participants will be admitted to the trial site in the evening of Day -1 of Visit 2 and of Day 9 Visit 3, and kept under close medical surveillance for at least 72 h following drug administration. After formal assessment and confirmation of their fitness, subjects will then be allowed to leave the trial site. On all other study days, subjects will be treated in an ambulatory fashion.

For details on time points and procedures for collection of plasma samples for PK analysis, refer to [Flow Chart](#) and [Section 5.3.2](#).

The safety measurements performed during the treatment period are specified in [Section 5.3](#) of this protocol and in the [Flow Chart](#). For details on times of all other trial procedures, refer to the [Flow Chart](#). AEs and concomitant therapy will be assessed continuously from screening until the end of trial examination.

6.2.3 Follow-up period and trial completion

For AE assessment, laboratory tests, recording of ECG and vital signs, and physical examination during the follow-up period, see [Sections 5.2.1](#) to [5.2.7](#).

Subjects who discontinue treatment before the end of the planned treatment period should undergo the EoTrial Visit.

All abnormal values (including laboratory parameters) that are assessed as clinically relevant by the investigator will be monitored using the appropriate tests until a return to a medically acceptable level is achieved. (S)AEs persisting after a subject's EoTrial Visit must be followed until they have resolved, have been sufficiently characterised, or no further information can be obtained.

7. STATISTICAL METHODS AND DETERMINATION OF SAMPLE SIZE

7.1 STATISTICAL DESIGN – MODEL

The main objectives of this trial are to investigate the relative bioavailability of

Part 1: 25 mg (single dose) of BI 425809 when given alone (Test 1, T1) compared with co-administration with 10 mg (multiple doses) of donepezil (Reference 1, R1), and

Part 2: 10 mg (single dose) of donepezil when given alone (Test 2, T2) compared with co-administration with 25 mg (multiple doses) of BI 425809 (Reference 2, R2),

following oral administration on the basis of the primary and secondary pharmacokinetic endpoints, as listed in [Section 2.1.2](#) and [2.1.3](#). The trial is designed to allow intra-subject comparisons and will be evaluated statistically by use of a linear model for logarithmically transformed PK endpoints.

The assessment of safety and tolerability is a further objective of this trial, and will be evaluated by descriptive statistics for the parameters specified in [Section 2.2.2.2](#).

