4.1.4 Drug assignment and administration of doses for each subject

This trial consists of two parts:

Part 1 is an open-label, two-treatment, two-period, one fixed sequence cross-over trial, in which all subjects will first receive BI 425809 (treatment A = Reference 1) alone and then again after multiple doses of donepezil (treatment B = Test 1).

The treatments to be evaluated in Part 1 are outlined in [Table 4.1.4: 1](#) below.

Table 4.1.4: 1 Part 1: Dosage and treatment schedule

Treatment	Substance	Formulation	Unit strength	Dosage	Total dose
A (Reference 1)	BI 425809	Tablet	25 mg	1 tablet (Day 1, Visit 2)	25 mg
B (Test 1)	Donepezil	Tablet	5 mg	1 tablet (Day 1-7, Visit 3) q.d. 2 tablets (Day 8-28, Visit 3) q.d.	245 mg
	BI 425809	Tablet	25 mg	1 tablet (Day 22, Visit 3)	25 mg

Part 2 has an open-label two-treatment, two-period, one fixed-sequence cross-over design. In Part 2 all subjects will first receive donepezil (treatment C = Reference 2) alone and then again after multiple doses of BI 425809 (treatment D = Test 2).

The treatments to be evaluated in Part 2 are outlined in [Table 4.1.4: 2](#) below.

Table 4.1.4: 2 Part 2: Dosage and treatment schedule

Treatment	Substance	Formulation	Unit strength	Dosage	Total dose
C (Reference 2)	Donepezil	Tablet	5 mg	2 tablets (Day 1, Visit 2)	10 mg
D (Test 2)	Donepezil	Tablet	5 mg	2 tablets (Day 10, Visit 3)	10 mg
	BI 425809	Tablet	25 mg	1 tablet (Days 1-24, Visit 3) q.d.	600 mg

Trial medication will be administered to fasted subjects only (for fasting periods please refer to [Section 4.2.2.2](#)). The investigator (or authorised designee) will administer the trial medication as an oral dose together with about 240 mL of water to subjects who are in a standing position. For drug administration, the so-called four-eye principle (two-person rule) should be applied. For this, one authorised employee of the trial site should witness the administration of trial medication, and – if applicable – its preparation (e.g. reconstitution), if correct dosage cannot be ensured otherwise.

In **Part 1**, subjects will be kept under close medical surveillance until 38 h following administration of BI 425809 on Day 1, Visit 2 and on Day 22 Visit 3. In addition subjects will remain under medical supervision for about 14 h following the first dose of donepezil on Day 1 Visit 3. This in-house surveillance period can be extended anytime if deemed necessary based on the medical judgement of the investigator.

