7.2 NULL AND ALTERNATIVE HYPOTHESES

The relative bioavailability of BI 425809 administered alone compared with co-administration with donepezil (Part 1) and the relative bioavailability of donepezil administered alone compared with co-administration with BI 425809 (Part 2) will be estimated by the ratios of the geometric means (test/reference), and their corresponding 2-sided 90% confidence intervals (CIs) will be provided. This method corresponds to the two one-sided t-test procedure, each at the 5% significance level. Since the main focus is on estimation and not testing, a formal hypothesis test and associated acceptance range is not specified.

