7.3.1 Primary endpoint analyses

Primary analyses

The statistical model used for the analysis of the primary endpoints will be an analysis of variance (ANOVA) model on the logarithmic scale. That is, the PK endpoints will be log-transformed (natural logarithm) prior to fitting the ANOVA model. The model used in both Part 1 and Part 2 will include effects accounting for the following sources of variation: subjects and treatment. The effect 'subjects' will be considered as random, whereas the effect 'treatment' will be considered as fixed. The model is described by the following equation:

$$y_{km} = \mu + s_m + \tau_k + e_{km}, \text{ where}$$

$$y_{km} = \text{logarithm of response measured on subject } m \text{ receiving treatment } k,$$

$$\mu = \text{the overall mean,}$$

$$s_m = \text{the effect associated with the } m^{\text{th}} \text{ subject, } m = 1, 2, \dots, n,$$

$$\tau_k = \text{the } k^{\text{th}} \text{ treatment effect, } k = 1, 2,$$

$$e_{km} = \text{the random error associated with the } m^{\text{th}} \text{ subject in who received treatment } k.$$

where $s_m \sim N(0, \sigma_B^2)$ i.i.d., $e_{km} \sim N(0, \sigma_W^2)$ i.i.d. and s_m, e_{km} are independent random variables.

Point estimates for the ratios of the geometric means (test/reference) for the primary endpoints (see [Section 2.1.2](#)) and their two-sided 90% confidence intervals (CIs) will be provided.

For each endpoint, the difference between the expected means for $\log(T)$ - $\log(R)$ will be estimated by the difference in the corresponding adjusted means (Least Squares Means). Additionally their two-sided 90% confidence intervals will be calculated based on the residual error from the ANOVA and quantiles from the t-distribution. These quantities will then be back-transformed to the original scale to provide the point estimate and 90% CIs for each endpoint.

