6. GENERAL ANALYSIS DEFINITIONS

6.1 TREATMENTS

For basic study information on treatments to be administered, assignment of treatment groups, and selection of doses, cf. Section 4 of the CTP.

Each subject is planned to be treated in two subsequent treatment periods in a fixed sequence order. There will be no washout-period between the two treatment periods.

Part 1:

All subjects will receive a single dose of BI 425809 alone in Visit 2 and a single dose of BI 425809 after multiple dosing of donepezil in Visit 3.

Table 6.1: 1 Dosage and treatment schedule part 1

Treatment	Substance	Formulation	Unit strength	Dosage	Total dose
A (Reference 1)	BI 425809	Tablet	25 mg	1 tablet (Day 1, Visit 2)	25 mg
B (Test 1)	Donepezil	Tablet	5 mg	1 tablet (Day 1-7, Visit 3) q.d. 2 tablets (Day 8-28, Visit 3) q.d.	245 mg
	BI 425809	Tablet	25 mg	1 tablet (Day 22, Visit 3)	25 mg

Part 2:

All subjects will receive a single dose of donepezil alone in Visit 2 and then a single dose of donepezil after multiple dosing of BI 425809 in Visit 3.

Table 6.1: 2 Dosage and treatment schedule part 2

Treatment	Substance	Formulation	Unit strength	Dosage	Total dose
C (Reference 2)	Donepezil	Tablet	5 mg	2 tablets (Day 1, Visit 2)	10 mg
D (Test 2)	BI 425809	Tablet	25 mg	1 tablet (Day 1-24, Visit 3) q.d.	600 mg
	Donepezil	Tablet	5 mg	2 tablets (Day 10, Visit 3)	10 mg

For statistical analyses of AEs, vital signs, safety laboratory data and visual tests the following separate analysis phases will be defined for each subject:

Table 6.1: 3 Analysis phases for statistical analysis of AEs, vital signs, safety laboratory data and visual tests, part 1

Study analysis phase	Label	Start	End
Screening	Screening part 1	Date of informed consent	Date/time of first administration of BI 425809
On treatment BI 425809	BI part 1	Date/time of first administration of BI 425809	Date/time of first administration of donepezil
On treatment donepezil	Don part 1	Combination of two phases: First phase: Date/time of first administration of BI 425809 + 11*24h (i.e. REP of BI425809 of 11 days) Second phase: Date/time of second administration of BI 425809 + 11*24h (i.e. REP of BI425809 of 11 days)	Combination of two phases: First phase: Date/time of second administration of BI 425809 Second phase: Date/time of last administration of donepezil + 15*24h (i.e. REP of donepezil of 15 days) or 00:00 a.m. on day after subject's trial termination date whatever occurs earlier

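### Do the swapped Test and Reference labels in Protocol Section 7.1 put the direction of the primary ratios in doubt?

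*Protocol*

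**What the plan says.** Protocol Section 4.1.4 defines the arms. In Part 1 subjects receive "BI 425809 (treatment A = Reference 1) alone and then again after multiple doses of donepezil (treatment B = Test 1"; in Part 2 they receive "donepezil (treatment C = Reference 2) alone and then again after multiple doses of BI 425809 (treatment D = Test 2". The drug alone is Reference and co-administration is Test, and the dosing tables in that section carry the same labels.

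Protocol Section 7.1 reverses this in both parts: "BI 425809 when given alone (Test 1, T1) compared with co-administration with 10 mg (multiple doses) of donepezil (Reference 1, R1" and "donepezil when given alone (Test 2, T2) compared with co-administration with 25 mg (multiple doses) of BI 425809 (Reference 2, R2".

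Protocol Section 7.2 attaches neither label to an arm, but its word order follows 7.1, with the Part 2 comparison described as "administered alone compared with co-administration with BI 425809 (Part 2) will be estimated by the ratios of the geometric means (test/reference". It also says that "a formal hypothesis test and associated acceptance range is not specified".

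Protocol Section 7.3.1 calls for "Point estimates for the ratios of the geometric means (test/reference) for the primary endpoints" and a log(T) minus log(R) contrast, without saying again which arm is T.

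SAP Section 6.1 refers to Section 4 of the protocol for treatments. Its text starts from the drug alone ("All subjects will receive a single dose of BI 425809 alone in Visit 2"), and its Tables 6.1: 1 and 6.1: 2 label A and C as Reference and B and D as Test. SAP Section 7.4.1 gives the ratios as B over A and D over C. SAP Section 7.5.2 analyses the secondary endpoint in the same way. SAP Section 3 names protocol Section 7 as its basis, and SAP Section 4 declares no change from the protocol's statistical methods.

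**The concern.** Within protocol Section 7, the only place that says which arm is T and which is R is 7.1, and it has them the wrong way round for an interaction study. Joined to the test/reference estimator of 7.3.1, it specifies alone over co-administration, the reciprocal of what the SAP computes. All four labels in 7.1 are swapped and 7.2 keeps the same order, so this is not one mistyped word. The SAP then claims full accordance with the protocol and does not mention the difference.

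The direction matters because the trial estimates and does not test: the ratio is the result. Protocol Section 1.4 expects that BI 425809, a weak CYP3A4 inducer, may lower donepezil levels. Under the 7.1 labels a fall would be printed as a ratio above 1. Someone writing results from Section 7 alone could describe the interaction backwards for AUC0-∞, Cmax and AUC0-tz in each part.

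**Working it through.** The documents give no expected ratio and no intra-subject CV, so there is no stated figure to reproduce. The check has two parts.

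**1. Which direction does each section give?**

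| Place | Test | Reference | Resulting ratio |
|---|---|---|---|
| Protocol 4.1.4 | B, D (co-administration) | A, C (alone) | co-administration / alone |
| Protocol 7.1 | alone | co-administration | alone / co-administration |
| Protocol 7.2 | not assigned; order implies alone | not assigned | alone / co-administration, by word order only |
| Protocol 7.3.1 | not assigned | not assigned | T/R, direction open |
| SAP 6.1 | B, D | A, C | co-administration / alone |
| SAP 7.4.1 | B, D | A, C | B/A and D/C, stated outright |

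Only 7.1 assigns reversed labels. The objectives in protocol Section 2.1.1 ask for the effect of the added drug on the drug measured, and Section 3.1 casts donepezil as perpetrator in Part 1 and victim in Part 2. Both fit co-administration over alone. The ratios covered number 3 endpoints × 2 parts = 6, and SAP 7.4.1 with 7.5.2 fixes all six.

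**2. What would a reversal change?**

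For paired data on the log scale, with r the ratio of geometric means:

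- 90% CI = r × exp(±h), where h = t(0.95, n−1) × s × √(2/n) and s = √ln(1 + CV²).
- Reversing the ratio gives 1/r with limits 1/upper and 1/lower. The half-width h does not change.

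Inputs: n = 18 (Part 1) and n = 14 (Part 2), from protocol Section 7.7, with all subjects completing. Assumed: r = 0.80 and CV from 10% to 30%.

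| Part | CV | Co-administration / alone | Alone / co-administration |
|---|---|---|---|
| 1 (n = 18) | 10% | 0.80 (0.755–0.848) | 1.25 (1.180–1.324) |
| 1 | 20% | 0.80 (0.713–0.897) | 1.25 (1.114–1.402) |
| 1 | 30% | 0.80 (0.675–0.948) | 1.25 (1.054–1.482) |
| 2 (n = 14) | 10% | 0.80 (0.748–0.855) | 1.25 (1.169–1.336) |
| 2 | 20% | 0.80 (0.701–0.913) | 1.25 (1.095–1.427) |
| 2 | 30% | 0.80 (0.657–0.974) | 1.25 (1.027–1.521) |

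At CV 20% in Part 2, upper over lower is 0.913/0.701 = 1.30 one way and 1.427/1.095 = 1.30 the other. Precision is identical, and an interval excludes 1 in one direction exactly when it does in the other. The model, the 90% level and the sample size (18 + 14 = 32) do not depend on the labels.

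**The case for a change.** The strongest case for acting is that the SAP says it rests on protocol Section 7, and that section read by itself yields the reciprocal. SAP Section 4 is where a departure is normally recorded, the SAP (20 September 2019) is later than protocol version 4.0 (29 May 2019), and one sentence would cost almost nothing. Where the ratio is the whole result, a reversed description would be a serious reporting error.

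The label conflict stands, and so does the arithmetic. The claim of an undeclared departure is weaker. The protocol holds two conflicting label sets, and the SAP follows the one in the section that defines the treatments, which SAP 6.1 cites. It also keeps every statistical method of 7.3.1: log transformation, ANOVA with random subject and fixed treatment effects, test/reference ratio of geometric means, and 90% interval. The accordance statement refers to statistical methods, and on those it is true.

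The reporting risk needs an author to take the labels from 7.1 and disregard the ratios named in the SAP, the SAP treatment tables and protocol 4.1.4. That is possible, but it is not a defect in the analysis plan. The intervals above show only that 1/x differs from x; they are not evidence that the wrong direction would be reported.

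**Conclusion.** This is a clerical slip in protocol Section 7.1, echoed by the word order of 7.2, and no change to the plan follows. SAP Section 7.4.1 settles the direction as co-administration over alone in both parts, so an analyst following the plan obtains the intended result for all six ratios. Relabelling, or adding a note to the SAP, would change no estimate, interval, sample size or conclusion, and with no acceptance range there is no decision to reverse. If the protocol is reopened for another reason the labels can be tidied then, but nothing depends on it.

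The conclusion rests on the text of SAP 7.4.1 and 7.5.2 and not on the assumed ratio or CVs, which serve only to show what a reversal would look like. The descriptions of amendments 1 and 2 do not list Sections 7.1 or 7.2 as changed. The description of amendment 3 was not available, but the text assessed is the current version, which already includes it.

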7.2 NULL AND ALTERNATIVE HYPOTHESES

The relative bioavailability of BI 425809 administered alone compared with co-administration with donepezil (Part 1) and the relative bioavailability of donepezil administered alone compared with co-administration with BI 425809 (Part 2) will be estimated by the ratios of the geometric means (test/reference), and their corresponding 2-sided 90% confidence intervals (CIs) will be provided. This method corresponds to the two one-sided t-test procedure, each at the 5% significance level. Since the main focus is on estimation and not testing, a formal hypothesis test and associated acceptance range is not specified.

7.3 PLANNED ANALYSES

Analysis sets

Statistical analyses will be based on the following analysis sets:

- Treated set (TS): The treated set includes all subjects who were randomized and treated with at least one dose of study drug. The treated set will be used for safety analyses.
- Pharmacokinetic parameter analysis set (PKS): This set includes all subjects in the treated set (TS) who provide at least one PK endpoint that was defined as primary or secondary and was not excluded due to a protocol deviations relevant to the evaluation of PK or due to PK non-evaluability (as specified in the following

subsection 'Pharmacokinetics'). Thus, a subject will be included in the PKS, even if he/she contributes only one PK parameter value for one period to the statistical assessment. Descriptive and model based analyses of PK parameters will be based on the PKS.

Adherence to the protocol will be assessed by the trial team. Important protocol deviations (IPD) categories will be suggested in the IQRM plan. IPDs will be identified no later than in the Report Planning Meeting, and the IPD categories will be updated as needed.

Pharmacokinetics

The pharmacokinetic parameters listed in [Section 2.1](#) for drug BI 425809 will be calculated according to the relevant SOP of the Sponsor ([001-MCS-36-472](#)).

Plasma concentration data and parameters of a subject will be included in the statistical pharmacokinetic (PK) analyses if they are not flagged for exclusion due to a protocol deviation relevant to the evaluation of PK (to be decided no later than in the Report Planning Meeting) or due to PK non-evaluability (as revealed during data analysis, based on the criteria specified below). Exclusion of a subject's data will be documented in the CTR.

Relevant protocol violations may be

- Incorrect trial medication taken, i.e. the subject received at least one dose of trial medication the subject was not assigned to
- Incorrect dose of trial medication taken
- Use of restricted medications

Plasma concentrations and/or parameters of a subject will be considered as non-evaluable, if for example

- The subject experienced emesis that occurred at or before two times median t_{max} of the respective treatment (Median t_{max} is to be determined excluding the subjects experiencing emesis),
- The subject experiences emesis at any time during the labelled dosing interval
- A predose concentration is $>5\%$ C_{max} value of that subject
- Missing samples/concentration data at important phases of PK disposition curve

Plasma concentration data and parameters of a subject which is flagged for exclusion will be reported with its individual values but will not be included in the statistical analyses. Descriptive and inferential statistics of PK parameters will be based on the PKS.

Only concentration values within the validated concentration range and actual sampling times will be used for the calculation of pharmacokinetic parameters. Concentrations used in the pharmacokinetic calculations will be in the same format provided in the bioanalytical report, (that is, to the same number of decimal places provided in the bioanalytical report).

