	7	144:00	18:00	Ambulatory visit ¹¹ , admin. 5 mg donepezil			x ⁸				x ^{2,7}		
	8	168:00	18:00	Ambulatory visit ¹¹ , admin. 10 mg donepezil	x ¹⁰			x ¹²	x ²	x ²	x ^{2,7}		
	9	192:00	18:00	Ambulatory visit ¹¹ , admin. 10 mg donepezil							x ^{2,7}		
	10	216:00	18:00	Ambulatory visit ¹¹ , admin. 10 mg donepezil							x ^{2,7}		
	11	240:00	18:00	Ambulatory visit ¹¹ , admin. 10 mg donepezil							x ^{2,7}		
	12	264:00	18:00	Ambulatory visit ¹¹ , admin. 10 mg donepezil	x ¹⁰				x ²	x ²	x ^{2,7}		
13	288:00	18:00	Ambulatory visit ¹¹ , admin. 10 mg donepezil							x ^{2,7}			
14	312:00	18:00	Ambulatory visit ¹¹ , admin. 10 mg donepezil			x ⁸				x ^{2,7}			

Visit	Day	Planned time (relative to first drug administration [h:min])	Approximate clock time of actual day [h:min]	Event and comment	Safety laboratory	PK _{plasma} (BI 425809)	PK _{plasma} Donepezil	Safety assessments	12-lead ECG ¹⁴	Vital signs (BP, PR) ¹⁴	Questioning for AEs and concomitant therapy ⁶	
3 (Treatment B)	15	336:00	18:00	Ambulatory visit ¹¹ , admin. 10 mg donepezil							x ^{2,7}	
	16	360:00	18:00	Ambulatory visit ¹¹ , admin. 10 mg donepezil	x ¹⁰			x ¹²	x ²	x ²	x ^{2,7}	
	17	384:00	18:00	Ambulatory visit ¹¹ , admin. 10 mg donepezil							x ^{2,7}	
	18	408:00	18:00	Ambulatory visit ¹¹ , admin. 10 mg donepezil							x ^{2,7}	
	19	432:00	18:00	Ambulatory visit ¹¹ , admin. 10 mg donepezil	x ¹⁰		x ⁸		x ²	x ²	x ^{2,7}	
	20	456:00	18:00	Ambulatory visit ¹¹ , admin. 10 mg donepezil			x ⁸				x ^{2,7}	
	21	480:00	18:00	Ambulatory visit ¹¹ , admin. 10 mg donepezil			x ⁸				x ^{2,7}	
	22	494:00	08:00	Admission to trial site	x ^{5,10}				x ¹²	x	x	x ^{2,7}
		504:00	18:00	Drug administration, 25 mg BI 425809 + 10 mg donepezil		x ⁸	x ⁸					x ^{2,7}
		504:30	18:30			x						
		505:00	19:00			x						
		506:00	20:00	240 ml fluid intake		x						
		507:00	21:00			x						
		507:30	21:30			x						
		508:00	22:00	240 mL fluid intake, Dinner, thereafter start of bed rest ¹⁶		x				x	x	x
		508:30	22:30			x						
		509:00	23:00			x						
	23	510:00	00:00			x						
		512:00	02:00			x						
		514:00	04:00			x						
		516:00	06:00	End of bed rest ¹⁶ , Breakfast ³		x				x	x	x
		528:00	18:00	Drug administration, 10 mg donepezil		x				x ²	x ²	x ^{2,7}
	24	540:00	06:00			x						x ^{2,7}
		542:00	08:00	Discharge ¹¹					x ¹²	x	x	x ⁷
		552:00	18:00	Ambulatory visit ¹¹ , admin. 10 mg donepezil		x ⁸						x ^{2,7}
	25	576:00	18:00	Ambulatory visit ¹¹ , admin. 10 mg donepezil	x ¹⁰	x ⁸	x ⁸		x ²	x ²	x ^{2,7}	

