1. INTRODUCTION

BI 425809 is a glycine transporter 1 (GlyT1) inhibitor that is being developed for symptomatic treatment of Alzheimer's Disease (AD) and cognitive impairment associated with schizophrenia (CIAS)

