Further undesirable effects of donepezil include common cold, anorexia, hallucinations, agitations, aggressive behavior, abnormal dreams and nightmares, liver dysfunction including hepatitis, minor increase in serum concentration of muscle creatine kinase, rhabdomyolysis, rash pruritus, muscle cramps, urinary incontinence, headache, fatigue, pain, and accident.

Donepezil

- Is likely to exaggerate succinylcholine-type muscle relaxation during anesthesia
- Should not be co-administered with other cholinergic agonists or antagonists
- Has minor or moderate influence on the ability to drive and use machines
- May have vagotonic effects on the sinoatrial and atrioventricular nodes manifesting as bradycardia or heart block
- As a cholinomimetic may cause bladder outflow obstruction although this was not observed in clinical trials with marketed Aricept (tradename of donepezil in the US)
- As a cholinomimetic may have the potential to cause seizures
- Should be used with care in patients with history of asthma or COPD as cholinomimetics may cause bronchoconstriction

Neuroleptic Malignant Syndrome (NMS):

NMS, a potentially life-threatening condition characterized by hyperthermia, muscle rigidity, autonomic instability, altered consciousness and elevated serum creatine phosphokinase levels, has been reported to occur very rarely in association with donepezil, particularly in patients also receiving concomitant antipsychotics. Additional signs may include myoglobinuria (rhabdomyolysis) and acute renal failure.

Cholinergic crisis:

Donepezil overdose can result in cholinergic crisis characterized by severe nausea, vomiting, salivation, sweating, bradycardia, hypotension, respiratory depression, collapse and convulsions. Increasing muscle weakness is possible and may result in death if respiratory muscles are involved.

For a more detailed description of the profile of BI 425809, please refer to the current Investigator's Brochure [[c02155957](#)] and for donepezil to the SmPC [[R18-3913](#)].

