4.1.1 Identity of the Investigational Medicinal Products

The characteristics of the trial products are given below:

Trial product 1:

Substance:	BI 425809
Pharmaceutical formulation:	Film coated tablet
Source:	BI Pharma GmbH & Co. KG, Germany
Unit strength:	25 mg
Posology:	Part 1: 0-0-1 Part 2: 1-0-0
Route of administration:	Oral
Duration of use:	Part 1: single dose on Day 1, Visit 2, and on Day 22, Visit 3 Part 2: multiple doses on days 1-24, Visit 3

Trial product 2:

Name:	Donepezil-HCl-ratiopharm®
Substance:	Donepezil
Pharmaceutical formulation:	Film-coated tablet
Source:	Ratiopharm GmbH, Germany
Unit strength:	5 mg
Posology:	Part 1: 0-0-1 (Days 1-7, Visit 3) and 0-0-2 (Days 8-28, Visit 3) Part 2: 2-0-0
Route of administration:	Oral
Duration of use:	Part 1: multiple doses on days 1-28, Visit 3 Part 2: single dose on Day 1, Visit 2 and on Day 10, Visit 3

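### Does the undefined labelled-dosing-interval emesis criterion in Protocol Section 7.3 make the Part 1 comparison one-sided?

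*Protocol*

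**What the plan says.** Under Pharmacokinetics, Protocol Section 7.3 lists examples of when a subject's concentrations or parameters are non-evaluable. Two of them concern vomiting:

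- "The subject experienced emesis that occurred at or before two times median" tmax of the respective treatment;
- "The subject experiences emesis at any time during the labelled dosing interval".

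Neither is restricted to a part, an analyte or a drug, and neither document defines the labelled dosing interval. The same section keeps a subject in the PK analysis set "even if he/she contributes only one PK parameter value for one period to the statistical assessment".

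In Part 1 (Protocol Section 4.1.4), "all subjects will first receive BI 425809 (treatment A = Reference 1) alone and then again after multiple doses of donepezil". Section 4.1.1 gives the donepezil dosing as "Part 1: multiple doses on days 1-28, Visit 3", with BI 425809 as one single dose in each period. The second profile starts on Day 22 of Visit 3 (Flow Chart: "Drug administration, 25 mg BI 425809 + 10 mg donepezil"). In Part 2 donepezil is the measured drug in both periods.

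The SAP has no emesis rule of its own. Section 7.4.1 works through inclusion and exclusion flags and refers to sponsor standards for PK analysis.

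**The concern.** A labelled interval suggests a product label, and only donepezil clearly has one. Protocol Section 1 says "BI 425809 is a glycine transporter 1 (GlyT1) inhibitor that is being developed for symptomatic treatment", and Section 1.2.2 sends the reader to the Investigator's Brochure for that compound "and for donepezil to the SmPC". On that reading the criterion has two possible meanings in Part 1. Either it has nothing to act on, because the measured drug has no label, or it acts through donepezil and so in treatment B only.

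In the second case a subject who vomits could lose the test value and keep the reference value. The within-subject comparison would then have fewer complete pairs. If those who vomit differ in exposure from the rest, the test/reference ratio could also shift. In Part 2 the once-daily interval contains the tmax window, which makes one of the two criteria look superfluous. The trial is open-label through data cleaning and analysis preparation (Protocol Section 4.1.5), so an undefined rule might be settled with the data in view.

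**Working it through.** **Part 2: are the criteria nested?** Protocol Section 1.2.2 gives a donepezil tmax of 3 to 4 h and once-daily dosing.

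- Twice tmax: 2 × 3 = 6 h to 2 × 4 = 8 h.
- Once-daily interval: 24 h.

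The 6 to 8 h window lies inside 24 h. The tmax criterion would add an exclusion only if median tmax exceeded 24/2 = 12 h. A criterion nested in another changes nobody's status, and both act alike in treatments C and D.

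**Part 1: what could the interval be?**

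| Reading | Treatment A | Treatment B |
|---|---|---|
| Label of BI 425809 | nothing | nothing |
| Nominal once-daily window after the BI 425809 dose | 24 h | 24 h |
| Donepezil interval after the Day 22 dose | nothing | 24 h |
| All donepezil doses during the second BI 425809 profile (504:00 to 648:00) | nothing | 7 × 24 = 168 h |
| All donepezil doses in Visit 3 | nothing | 28 × 24 = 672 h |

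The first two rows treat the periods equally. The second has some support: Section 4.1.1 gives BI 425809 a Part 1 posology in the same daily notation as donepezil, and Section 4.1.6 says its tablets are labelled, with the label description in the site file. The last two rows stretch a singular interval into 7 or 28 of them. Under 672 h, vomiting on Day 3 would void a profile that starts on Day 22. That leaves the third row as the realistic one-sided reading. It adds only vomiting between twice the median tmax and 24 h after a single dose.

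**Size if test values alone are lost.** The documents give neither a vomiting rate nor variances for the endpoints, so the following is assumed: k = 1, 2 or 4 test values lost of N = 18, a between/within variance ratio r from 0.5 to 4, and a within-subject CV of 20%.

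With n = N − k complete pairs and a = k/(N(1 + r)), the variance of the log difference under the planned mixed model, in units of the within-subject variance, is

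V = 2/n + a²(1 + r)(1/k + 1/n) − 2a/n.

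The half-width is t(0.95, n − 1) × √V × SD_W, with SD_W = √ln(1 + 0.2²) = 0.198. With nothing lost, V = 2/18 = 0.1111, the half-width is 1.740 × 0.3333 × 0.198 = 0.115, and the upper factor is exp(0.115) = 1.122.

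If the subjects who lose a test value lie one between-subject SD above the rest, the test/reference ratio is multiplied by exp(−(k/N) × SD_W × √r/(1 + r)). The term √r/(1 + r) is largest at r = 1, where it equals 0.5. For k = 2 that gives exp(−0.111 × 0.198 × 0.5) = 0.989.

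| Test values lost | V | Half-width relative to 18 pairs | Upper 90% factor | Shift in ratio |
|---|---|---|---|---|
| 0 | 0.1111 | 1 | 1.122 | none |
| 1 | 0.1155–0.1170 | 1.023–1.030 | 1.125–1.126 | 0.995–0.996 |
| 2 | 0.1204–0.1236 | 1.049–1.063 | 1.128–1.130 | 0.989–0.991 |
| 4 | 0.1323–0.1397 | 1.111–1.141 | 1.136–1.140 | 0.978–0.983 |

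Four losses is an upper bound set for illustration. In the sponsor's earlier donepezil interaction trial (Protocol Section 1.2.2) vomiting is not among the most frequent drug-related events named, and the lowest frequency named there is 22.2% of 18, which is 4 subjects. A loss that large would be plausible only under the 672 h reading.

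**The case for a change.** The best case for a change is that it costs little. Three or four sentences in SAP Section 7.4.1 could name the dose and window for each part and apply them equally to both periods. Vomiting is a known effect of donepezil, and nausea affected 55.6% of subjects (10 of 18) in Part 1 of the earlier interaction trial, so the case may arise. A scope fixed in advance would remove a choice otherwise made with open-label data at hand.

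It stands that the term is undefined and that a product-label reading is one-sided in Part 1. Three points weaken the rest. First, the one-sided reading is not forced, since a nominal 24 h window after the BI 425809 dose is symmetric. Second, one-sidedness would not by itself be an error. Donepezil is present only in treatment B by design, so any check that it was absorbed can act only there, and tying the criteria to the BI 425809 dose alone is a preference. Third, the one-sided 24 h window opens after 21 days of donepezil. In the 28-day healthy-volunteer study described in Protocol Section 1.2.2, adverse events were transient and resolved during continued treatment. As for Part 2, the overlap of the two criteria excludes nobody extra, so there is nothing to correct.

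**Conclusion.** No change is needed. What remains is an undefined term in a list that the protocol presents as examples. Protocol Section 7.3 and SAP Sections 6.6 and 7.4.1 refer PK calculation, missing data and exclusions to sponsor standards, which were not available here and may define the interval. Protocol-deviation exclusions are decided by the Report Planning Meeting, every exclusion is documented in the trial report, and excluded individual values are still shown. A pharmacokineticist would read the criterion in relation to the dose being profiled. A reader could also see if only test-period values had been dropped.

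On the assumptions above, one or two test-only losses widen the interval by 2% to 6% on the log scale and shift the ratio by about 1% at most. Protocol Section 7.2 sets no acceptance range, so no pass/fail decision depends on this. These sizes rest on assumed losses, variance ratio and CV, because the documents give none of them. The conclusion would need another look only if the sponsor standard prescribed a long, donepezil-based window for Part 1.
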